10.1 Definitions

Term	Definition
Adverse Event (AE)	Any untoward medical occurrence in a study participant which is considered to be possibly related to brace treatment, or com- plications arising from spinal surgery.
Unexpected AE/SAE	An adverse event or serious adverse event which has not been pre-specified as expected.
Serious Adverse Event (SAE)	 An AE which is serious, defined as any untoward medical occurrence or effect that: Results in death Is life-threatening* Requires hospitalisation or prolongation of existing inpatients' hospitalisation** Results in persistent or significant disability or incapacity Is a congenital anomaly/birth defect Is otherwise considered medically significant by the investigator***
Related AE/SAE	An AE or SAE which is related to a research procedure
Notable Event	An event of particular interest that does not necessarily meet the criteria for seriousness but requires expedited reporting as per the protocol.

*The term life-threatening in the definition of a serious event refers to an event in which the patient is at risk of death at the time of the event; it does not refer to an event that hypothetically might cause death if it were more severe, for example, a silent myocardial infarction.

**Hospitalisation is defined as an inpatient admission, regardless of length of stay, even if the hospitalisation is a precautionary measure for continued observation. Hospitalisations for a pre-existing condition, that has not worsened or for an elective procedure do not constitute an SAE.

***Other important medical events that may not result in death, be life-threatening, or require hospitalisation may be considered a serious adverse event/experience when, based upon appropriate medical judgement, they may jeopardise the patient and may require medical or surgical intervention to prevent one of the outcomes listed in this definition.

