To be eligible for the study, none of the following crite should be met: 1. Previous bracing or spinal surgery; 2. Child or parent is unable to adhere to trial p	ıly
should be met: 1. Previous bracing or spinal surgery; 2. Child or parent is unable to adhere to trial p	
 Previous bracing or spinal surgery; Child or parent is unable to adhere to trial p 	ia
2. Child or parent is unable to adhere to trial p	
cedures or complete follow-up.	0-
Intervention & control groups The intervention group will receive a NTB, worn for	8-
12 hours a day, whilst in bed at night.	
The control group will receive a FTB, worn for 20-	24
hours a day. This is the current standard of care.	
Primary outcome The binary primary outcome is Cobb angle progressi	on
to 50 degrees or more before skeletal maturity (Rise	er
stage 4 in girls and Risser stage 5 in boys which is tre	at-
ment failure; or	
Skeletal maturity without this degree of Cobb angle p	·0-
gression is treatment success.	
Secondary outcomes Patient-reported outcomes:	
1. Scoliosis Research Society 22 questionnaire;	
2. Paediatric health related quality of life, measured u	S-
ing the CHU9D;	
3. Bad Sobernheim Stress Questionnaire (BSSQ)	а
brace specific questionnaire assessing the psycholo	
cal effects of bracing;	۰ ر
4. Revised Children's Anxiety and Depression Sci	ıle
(RCADS 25);	m
5. PROMIS Paediatric Sleep Disturbance Short Fo	

	6 PROMIS Paediatric Sleep Related Impairment Short Form 4a
	7. Modified Client Satisfaction with Device module of
	the Orthotics and Prosthetics Users' Survey (CSD-
	OPUS)
	8. Education information assessed using a bespoke
	questionnaire.
	Parent Questionnaires:
	12. Patient Cost Questionnaire, using a bespoke ques-
	tionnaire
	13. Resource Use Questionnaire, using a bespoke
	questionnaire;
	14. School attendance.
	Clinical:
	15. Radiological measures: Cobb angle, curve type,
	curve apex, Risser sign, in-brace Cobb angle, frontal
	plane balance, apical vertebral rotation, apical vertebral
	translation;
	16. In-brace correction;
	17. Menarchial age;
	18. Details of any surgery for scoliosis correction;19. Other treatments prescribed to treat scoliosis, e.g.
	scoliosis specific exercises;
	20. Complications (e.g. skin irritation) and Serious Ad-
	verse Events;
	21. Brace compliance, assessed using the implantation
	of a temperature sensor in the FTB or NTB;
	22. Treatment switching, including reason for doing so.

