Before randomisation, patients will be asked if they have a preference for which brace they would want. This question will be asked by the site research team and documented on the study database, rather than a specific questionnaire.

All SAEs occurring up to 2 years post skeletal maturity (end of involvement in the trial) will be reported to the CTRU/Sponsor on learning of their occurrence. Delegated site trial staff will be responsible for recording all adverse events and making them known to the Principal Investigator (see Section 10).

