10.2 Recording and reporting

AEs and SAEs are defined as an event that occurs after the patient has provided written informed consent for trial entry and prior to their completion of the trial.

AEs will be recorded on the adverse event report form, where these are considered to be possibly related to brace treatment, or complications arising from spinal surgery, within the participant CRF, including those that fulfil the criteria for being serious (see section 10.1). Sites are asked to enter all available information onto the study database as soon as possible after the site becomes aware of the event.

SAEs will require more detailed information to be recorded. In such cases, the event must also be reported to the Sheffield CTRU within 24 hours of the site becoming aware of the event. The CTRU will coordinate ongoing monthly reporting to the Sponsor, or as soon as possible if unexpected SAE. All SAEs will be reported, not just those related to brace treatment, or complications arising from spinal surgery.

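### Section 10.1 makes causality part of what an SAE is, which contradicts the all-SAE reporting rule in 10.2, and its definition of related leaves out the brace

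*Protocol*

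**What the plan says.** Four statements in the protocol bear on which events are captured.

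- **AE (10.1):** "Any untoward medical occurrence in a study participant which is considered to be possibly related to brace treatment", with complications of spinal surgery added.
- **SAE (10.1):** "An AE which is serious, defined as any untoward medical occurrence or effect that" meets one of the listed seriousness criteria.
- **AE form (10.2):** "AEs will be recorded on the adverse event report form, where these are considered to be possibly related to brace treatment", or are complications of spinal surgery. The same sentence extends this to events that meet the seriousness criteria and refers back to 10.1.
- **SAE reporting (10.2):** "All SAEs will be reported, not just those related to brace treatment, or complications arising from spinal surgery".

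Two other sections give the SAE rule with no condition on cause. Section 8.2 says "All SAEs occurring up to 2 years post skeletal maturity (end of involvement in the trial) will be reported to the CTRU/Sponsor". Section 10.4 asks for notification of every SAE that is not exempt.

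Relatedness has its own row in 10.1. A related event is "An AE or SAE which is related to a research procedure". The protocol does not say what counts as a research procedure.

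**The concern.** Whether an event is an SAE should depend on what happened to the participant. Its cause is a separate judgement, made afterwards. Section 10.1 puts the causal judgement first: an event must be thought possibly due to the brace, or come from spinal surgery, before it is an AE at all, and only an AE can become an SAE.

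Staff at a site use 10.1 to decide whether they have an SAE. If they apply it literally and judge the event unrelated, they stop there and never reach the instruction in 10.2 to report all SAEs. Section 4.1 states that treating clinicians are not blinded, so this judgement is made knowing the allocation. The DMEC and TSC reports (10.6) and the by-arm safety tables (11.2) could then combine sites that used different capture rules.

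The relatedness row raises a smaller problem. The harms that 10.3 lists as expected are brace pain and device-related pressure injury, yet the definition of related does not name the brace.

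**Working it through.** No arithmetic applies. The check sets the definitions against the reporting rules.

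**Step 1. The SAE definition.** Let A be the events considered possibly related to brace treatment or arising from spinal surgery. Let S be the events that meet a seriousness criterion.

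- AE in 10.1 = A.
- SAE in 10.1, opening words (a serious AE) = A and S.
- SAE in 10.1, continuation (any untoward occurrence that is serious) = S.

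These two sets are equal only if every serious event is in A. The row therefore holds two different definitions.

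**Step 2. Test against 10.2.** Section 10.2 requires SAEs outside A to be reported.

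- Under the opening words, SAEs outside A = (A and S) but not A = none.
- Under the continuation, SAEs outside A = S but not A, which is the group 10.2 has in mind.

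So the 10.2 sentence has content only under the second half of the SAE row. Under the first half it asks for events that cannot exist.

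**Step 3. Follow one event.** Take an unplanned admission that the site judges unrelated to brace or surgery.

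| Rule | Captured? |
|---|---|
| 10.1, AE row | No |
| 10.1, SAE row, opening words | No |
| 10.1, SAE row, continuation | Yes |
| 10.2, AE form, serious events included | No |
| 10.2, all-SAE sentence | Yes |
| 8.2 and 10.4, all SAEs | Yes, if the event is first recognised as an SAE |

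Sections 10.1 and 10.2 each contain both answers.

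**Step 4. The relatedness row.** Three readings of research procedure are open.

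- Neither brace is one: a full-thickness pressure injury caused by a brace, which 10.3 marks as an SAE, is not related in either arm.
- Both braces are: the label works, but the text does not say so.
- Only the NTB is: the label differs by arm.

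**Step 5. Where the label is used.** Faster reporting to the sponsor depends on the event being unexpected (10.2). The 24-hour rule depends on seriousness and the 10.3 exemptions. The DMEC and TSC receive all AEs and SAEs (10.6). The analysis tabulates AEs and SAEs by arm and states no split by relatedness (11.2). No stated reporting or analysis step depends on the label.

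**The case against.** The strongest reply is that the operative instruction is clear. Section 10.2 addresses unrelated SAEs directly and says to report them, 8.2 and 10.4 agree, and the second half of the SAE row carries no causal test. A trained site would probably report all SAEs. Much of this stands: the intent is not in doubt, and it cannot be said that serious events will be missed. It does not remove the defect, because 10.2 also sends serious events through the causal filter on the AE form with a reference back to 10.1, and 10.1 is where a site decides whether the reporting rule applies.

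Limiting non-serious AEs to those possibly related is a defensible choice in a pragmatic trial and is not criticised here.

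Three stronger readings may tempt a reader, and the protocol does not support them.

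- **A further contradiction in 8.2.** "Delegated site trial staff will be responsible for recording all adverse events" looks like an unrestricted rule for AEs, but the sentence refers to Section 10, so it can be read with the Section 10 meaning of the term.
- **Bias against the NTB.** The Trial Summary says of the FTB "This is the current standard of care", and 6.4 says the NTB is not available on the NHS, so one could infer that only the NTB is a research procedure. But Section 6 treats both braces as trial treatment, the recording filter and the 10.3 exemptions are the same in both arms, and the label drives no stated step. Different classification by arm is possible, not established.
- **A count of lost events.** Any such figure needs an admission rate, which the protocol does not give. It would also have to assume that every admission is unrelated and that every site ignores 10.2.

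**Conclusion.** The point holds as a contradiction in the SAE capture rule, with a second, smaller defect in the definition of related. It should be corrected, but it does not threaten the primary analysis.

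The events affected are serious events judged unrelated to brace or surgery, in either arm. Their number cannot be derived from the protocol. Any practical effect assumes that at least one site applies the opening words of the 10.1 SAE row, or the 10.2 form rule, literally; site training or form guidance not shown here may already prevent that.

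The relatedness wording means that an injury caused by a brace need not be labelled related in either arm. On the text shown, that affects the label only, not what is recorded, reported or tabulated.

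**What to change.** 1. In 10.1, define an SAE as any untoward medical occurrence that meets a seriousness criterion, regardless of cause, and remove the dependence on the AE row.
2. Keep the condition of possible relation to brace treatment or spinal surgery only as the recording filter for non-serious AEs. In 10.2, remove it for serious events.
3. Define related identically for both arms: possibly related to the allocated brace (FTB or NTB) or to a research procedure.

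This follows the intent already stated in 10.2 and leaves treatment, endpoints and sample size unchanged. The cost is an edit to 10.1 and 10.2, a line of site guidance, and a modest rise in forms for unrelated SAEs at any site now using the narrower definition. Sites already reporting all SAEs would send no additional SAE reports.

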10.2 Recording and reporting

AEs and SAEs are defined as an event that occurs after the patient has provided written informed consent for trial entry and prior to their completion of the trial.

AEs will be recorded on the adverse event report form, where these are considered to be possibly related to brace treatment, or complications arising from spinal surgery, within the participant CRF, including those that fulfil the criteria for being serious (see section 10.1). Sites are asked to enter all available information onto the study database as soon as possible after the site becomes aware of the event.

SAEs will require more detailed information to be recorded. In such cases, the event must also be reported to the Sheffield CTRU within 24 hours of the site becoming aware of the event. The CTRU will coordinate ongoing monthly reporting to the Sponsor, or as soon as possible if unexpected SAE. All SAEs will be reported, not just those related to brace treatment, or complications arising from spinal surgery.

10.3 Study specific exemptions

Scoliosis surgery is an expected outcome for this patient group. This will not be recorded as an SAE, and will be collected elsewhere on the CRF.

Adverse events which are expected with brace treatment, are listed below. If any of these occur during the trial, and also meet the criteria for being an SAE, they will be exempt from reporting within 24 hours. Such AEs and SAEs will still be reported, but removing this expedited timeframe will reduce the burden on sites.

- Severe pain from the brace requiring brace adjustment or re-design.
- Medical Device Related Pressure Ulcer (Injury)(53). We will follow the European Pressure Ulcer Advisory Panel definition but dividing Stage 2 into two commonly seen categories with spinal brace treatment. The following should be recorded as an AE but if it meets the criteria for an SAE, will not be reported within 24 hours:
 - o Stage 1: Skin erythema which is non-blanching with pressure
 - Stage 2a: Superficial abrasions

AEs/SAEs meeting the following definitions **will be reported** in line with requirements in section 10.4.

- Stage 2b: Partial thickness skin loss
- Stage 3: Full thickness skin loss (dermis and epidermis) (SAE)
- Stage 4: Full thickness tissue loss (SAE)

10.4 SAE notification procedure

CTRU should be notified of all SAEs (unless exempt), within 24 hours of the investigator becoming aware of the event.

BASIS Study

The SAE form must be completed by the investigator or delegated member of the research team. All SAE forms must be sent by email to [contact]. Receipt of the initial report should be confirmed within one working day. The site research team should contact the study team at CTRU if confirmation of receipt is not received within one working day.

Initial SAE reports must be followed by detailed reports when further information becomes available. Participants must be followed up until clinical recovery is complete and laboratory results have returned to normal or baseline, or until the event has stabilized. Follow up information will be provided on an SAE report marked as such.

10.5 CTRU responsibilities

The Sponsor usually delegates CTRU responsibility for the reporting of SAEs to the regulatory authorities and the research ethics committee, as appropriate. CTRU will also keep all investigators informed of any safety issues that arise during the course of the study.

10.6 SAE additional reporting

The DMEC and TSC will also receive information on all AEs and SAEs, at a frequency agreed with each committee and documented in the appropriate charter/terms of reference. Should these committees require any further information on any AEs or SAEs, this will be communicated to the site by CTRU.

11. Statistics

11.1 Sample size

In the BrAIST trial 28% of braced patients progressed to 50 degrees or more before skeletal maturity, which was the primary endpoint (5), so assuming this for the FTB group, with a non-inferiority margin of 11%, 90% power, 2.5% one-sided significance level and 10% attrition, the study will require 780 participants (390 per group).

This margin was chosen based on participants and parents. They have stated there is considerable functional and psychological benefit from not wearing braces during the daytime. During both PPI focus groups patients have expressed mixed views about FTB, which some were being treated with, and the concept of NTB. Approximately 50% of the group expressed a preference for a NTB. In our SAUK survey, 60% said

they would prefer a NTB compared to 27% for a FTB (and 7% no brace, 6% no answer).

11.2 Statistical Analysis

The trial will be analysed and reported according to CONSORT guidelines for noninferiority designs (54).

The ITT population (and safety) populations will consist of all participants who consent and are randomised to receive FTB or NTB.

The per protocol (PP) will be defined for participants in the FTB group, as

receiving the FTB treatment as documented in the study protocol (see Section 6)
 Complying and adhering to the treatment they were assigned to. Compliance with FTB would mean wearing the brace for average of >12.9hrs/day (= >65% of the minimum prescribed time) over the post-randomisation follow-up period.

For the NTB group, the PP population will be defined as

1) receiving the NTB treatment as documented in the study protocol

2) Complying and adhering to the treatment they were assigned to. Compliance with NTB would mean wearing the brace for average of >5.2hrs/day (= >65% of the minimum prescribed time) over the post-randomisation follow-up period.

Patients who cross-over from NTB to FTB will be removed from the PP population for the analysis of the primary outcome.

The binary primary outcome is curve progression to 50 degrees or more (treatment failure) before skeletal maturity and skeletal maturity without this degree of curve progression (treatment success). Non-inferiority for the primary outcome will be declared if the two-sided 95% confidence interval (equivalent to a one-sided 97.5%) for the risk difference in the event rate of progression to 50 degrees between the NTB group and the FTB group does not exceed 11%. The analysis will be completed using a Generalized Linear Model (GLM) with binomially distributed response and identity link (55) adjusted for baseline covariates (site, skeletal maturity Risser score 0, 1 or 2, and Cobb angle). This will be conducted on both an intention-to-treat (ITT) population and per protocol (PP) basis. The adjusted differences in failure rates, along with 95% con-fidence intervals will be calculated and presented.

Missing data

For the primary outcome, curve progression to 50 degrees or more (treatment failure) and skeletal maturity without this degree of curve progression (treatment success) any missing outcome data will be imputed through a default "worst" case scenario (i.e. assume treatment failure) and "best" case scenario (i.e. assume treatment success) and the results compared with the available data analysis.

Time to event analysis will also be completed on the primary outcome data. This will also be considered on an ITT and PP basis. For the PP analysis non-adherers will be censored at the time at which they begin to non-adhere - what is defined as non-adherence will be pre-specified after discussion with clinical experts, including the DMEC and TSC. To account for potential time dependent confounding an inverse probability weighting (IPW) approach will be used to estimate the PP treatment effect (56). This is important because non-adherence might be related to prognosis, and therefore censoring non-adherers may represent informative censoring and induce selection bias. In addition, an analysis that adjusts specifically for any treatment crossover that occurs will be undertaken. The IPW approach will again be used for this analysis, as will a rank preserving structural failure time model (RPSFTM), in line with recommendations made by the National Institute for Health and Care Excellence (NICE) Decision Support Unit for adjusting (when relevant) for treatment switching in randomised controlled trials (57).

For the secondary outcome of Cobb angle, a longitudinal analysis of all time points will be used to assess the difference on a non-inferiority basis between the two groups. This analysis will use a linear mixed-model including the all available time points, other important potential baseline confounders (such as Risser score 0, 1 or 2, and baseline Cobb angle) and site as a random effect.

Patient reported repeated outcome measures will be assessed over time using summary measures such as Area Under the Curve on a superiority basis (58).

Data on adverse events and serious adverse events will be tabulated at the end of the trial and presented by treatment arm. This will include the number and percentage of participants reported as having any adverse event.

Detailed statistical methods for all outcomes and scenarios will be described in a related trial Statistical Analysis Plan written before the data is analysed according to the Sheffield CTRU standard operating procedures approved by the TSC and DMEC (both of which have independent statistical members).

Economic evaluation

Different bracing options are likely to result in different costs, whether due to intervention costs, other related healthcare costs, or subsequent surgery costs. Also, it is conceivable that different bracing options will result in different health-related quality of life; even if NTB results in poorer control of scoliosis, there could be offsetting improvements in quality of life due to not having to wear a FTB (conversely, there could be reductions in quality of life if control of scoliosis is poor). Therefore, it is highly relevant to conduct an economic evaluation alongside this trial. We will estimate the relative cost-effectiveness (CE) of NTB compared to FTB and will present results for two key outcome measures: cost-per quality adjusted life years (QALYs) gained, and cost-per surgery avoided. Usually only cost per QALY results are presented for economic evaluations, but in this case, where a critical outcome is the avoidance of surgery, we consider it relevant to also present cost per surgery avoided – particularly because the patient population is children and so cost per QALY results will require considerable extrapolation beyond the end of the trial. It will be assumed that scoliosis of 50 degrees or greater will result in surgery.

The primary CE analyses will take an NHS and personal social services perspective in accordance with NICE (59), and the primary cost per QALY analysis will take a lifetime perspective, with proportions of patients who do and do not progress to surgery estimated based upon scoliosis degrees. A secondary analysis will present cost per QALY results restricted to the trial follow-up period. Intervention costs will be based upon information collected using CRFs, to include the type of brace and the resource use associated with fitting it. Wider resource use will include any other health care costs incurred (such as primary care appointments, and hospital admissions or appointments) that are related to the brace or scoliosis. Information on these will be collected via a bespoke resource use questionnaire. Unit costs will be derived from national sources (60,61). Health related quality of life (HRQL) will be estimated using the CHU9D questionnaire (42), specifically developed for children aged between 7 and 17. Both measures can be used to estimate preference-based utility scores, allowing QALYs to be derived. For the evaluation that takes a lifetime perspective we will extrapolate beyond adolescence using utility scores based on a search of the literature. A supplementary analysis from a broader perspective, incorporating societal costs associated with parents' time taken off work and travel costs associated with hospital visits related to the brace or scoliosis, will be included. Information on these costs including on private health care costs associated with the brace or scoliosis will be collected via a patient cost questionnaire.

The primary CE analyses will be based on ITT-based estimates of effectiveness. However, analyses that incorporate findings from the PP analysis and/or analyses that adjust for treatment crossover will be undertaken, if these are deemed relevant given the protocol violations and treatment switches that are observed in the trial, and given the decision problem defined for the economic evaluation; that is, whether initiating treatment with NTB represents a cost-effective use of NHS resources compared to initiating treatment with FTB. Results will allow for uncertainty using bootstrapping and probabilistic sensitivity analysis. Incremental CE ratios will be presented.

12. Ancillary sub-studies

